5. AMENDMENTS AND UPDATES

Number	Date	Section of the study protocol	Amendment or update	Reason
1	26 May 2023	Abstract	Removal of analyses involving comparison of empagliflozin vs GLP1RA.	Phase 1 analyses indicated differences in treatment exposure between patients prescribed empagliflozin compared to those prescribed GLP1RAs (i.e., greater proportion of patients prescribed 4+ prescriptions observed for GLP1RA over follow up)
		8.0 Research questions and objectives		
		9.1 Study design		
		9.2.2.2 Flowchart		
		9.3.1 Exposures	Timelines/milestones extended	Update protocol to reflect study progress at time of amendment
			EU PASS Register Number added	Number not available at time of initial protocol approval
		9.3.2.2 Outcomes	Added study outcome	The composite outcome of MI + stroke+all-cause death+ cardiovascular revascularization was previously in the protocol but the composite MI+stroke +all-cause death was added

Proprietary confidential information © 2023 Boehringer Ingelheim International GmbH or one or more of its affiliated companies

Number	Date	Section of the study protocol	Amendment or update	Reason
		9.7.3.0 Sensitivity analysis	Addition of acute HHF codes as a sensitivity analysis	The initial broader codelist for HHF will be performed but a sensitivity analysis only including HHF that indicate acute HF will be examined.

6. MILESTONES

Milestone	Planned Date
IRB/IEC approval	June 2021
Start of data collection	May 2022
End of data collection	July 2022
<Registration in the EU PAS register>	June 2022
Final results ready	Q4 2023
Final report of study results:	Q4 2023

7. RATIONALE AND BACKGROUND

The global prevalence of diabetes has increased nearly 4-fold in the last forty years and this increase is projected to continue [R21-4492]. Diabetic kidney disease (DKD) affects 30-40% of persons with diabetes and is the leading cause of end-stage renal disease (ESRD) in the United States [P18-00615, R19-1661].] The development of DKD substantially increases the risk of mortality for persons with diabetes [R13-0685].] Empagliflozin and other sodium-glucose cotransporter 2 inhibitors (SGLT2i) have emerged as the first promising advance in the care of DKD for nearly two decades. While kidney and cardiovascular outcomes trials have demonstrated clear cardiorenal benefit for empagliflozin and SGLT2i above standard care and renin-angiotensin-aldosterone axis blockade [P15-09840, P16-06807, R19-1356, R21-1080],] no definitive study has compared the effectiveness of empagliflozin to other anti-hyperglycemic therapies. Since some of these therapies have putative cardiorenal benefits and risks [R18-1139, R17-1732, R21-4493], a direct comparison of empagliflozin and SGLT2i to these therapies is imperative.

In addition, the EMPRISE US study [P21-10532] used diagnostic coding from claims data to identify incident cases of end stage renal disease (ESRD) as the main renal outcomes and assessed the comparative effectiveness of empagliflozin vs DPP4 inhibitors. The current study builds upon the EMPRISE US study by also including key aspects of laboratory data that allow for assessment of eGFR-based renal outcomes and analyses of CKD cohorts defined by eGFR levels. This is a relevant adaptation to the EMPRISE US study methodology in that use of eGFR assessments of renal function are a more sensitive approach for categorizing CKD stages and monitoring changes in renal function over time. If feasible, this study will also include comparisons of risk for study outcomes between empagliflozin or SGLT2i compared to both DPP4 inhibitors and GLP1RAs. GLP1RA was not included in the EMPRISE studies as a comparison group.

8. RESEARCH QUESTION AND OBJECTIVES

The primary purpose of this research study is to determine the cardiovascular and renal effectiveness and safety of empagliflozin compared to DPP4i in patients with T2D in the

- Overall cohort,
- Patients with established kidney disease (DKD cohort), and
- Patients without established kidney disease (non-DKD cohort).

The secondary purpose of this research study is to determine the cardiovascular and renal effectiveness and safety of any SGLT2i compared to GLP1RA

9. RESEARCH METHODS

9.1 STUDY DESIGN

This will be a non-interventional comparative effectiveness and safety study, using existing (secondary) data from up to 20 US health systems that have mapped their electronic health record data to the PCORnet Common Data Model (CDM). The study period will be 1 January 2014 through 31 December 2021, which includes data during the COVID-19 pandemic. There will be an assessment of COVID-era data for quality purposes, and we will perform a sensitivity analysis excluding all data available from March 2020 to the end of the study period.

The primary objective of the study will include patients with T2D who initiate use of empagliflozin or DPP4i without prior use of either drug [class]. The primary analysis will compare patients with T2D initiating empagliflozin to patients with T2D initiating DPP4i.

The secondary objective of the study will include an additional cohort of patients: those with T2D who initiate use of any SGLT2i or GLP1RA without prior use of either drug class.

Propensity score weighting (overlap weighting [[R20-1964](#), [R21-4495](#)]) will be used to balance covariates between two treatment groups in each comparison (empagliflozin vs DPP4i; SGLT2i vs GLP1RA). With overlap weighting, the resulting reweighted sample targets the subpopulation of patients with the most overlap in covariates across the two treatment groups. Patients in this subpopulation have substantial probability to be assigned to either treatment of interest, and therefore represent patients for whom there is clinical equipoise for treatment assignment. Propensity score models will be developed, and the reweighted populations will be assessed to ensure cross-treatment group covariate balance within both the DKD and non-DKD subgroups, as well as for the overall cohorts using methods of Yang et al [[R21-4497](#)]. Additional details about propensity score modeling and reweighting are provided in the section on Data Analysis.

Study feasibility will be evaluated after data collection has occurred. If the final sample size does not meet the required sample size for 80% power, the planned sensitivity and subgroup analyses will be removed from the final study report. The primary analyses will still be assessed but in an exploratory capacity.

9.2 SETTING

9.2.1 Study sites

This study will utilize high-quality renal function laboratory data available in medical electronic health records from approximately 20 health systems in the US that have mapped their data to the PCORnet Common Data Model (CDM). Sites meeting PCORnet data curation quality checks will be eligible to participate in this study.

9.2.2 Study population

The analysis will include adults (≥ 18 years) with type 2 diabetes with or without kidney disease in the US. To study real-world treatment patterns, the study population will include a broad spectrum of new users of empagliflozin, SGLT2i, DPP4i or GLP1RA. The following inclusion and exclusion criteria will be used for each two-arm comparison:

9.2.2.1 Inclusion criteria

Inclusion criteria:

- Patients ≥ 18 years old,
- Having a diagnosis of type 2 diabetes in 12 months before the index date (defined as the date of initiation of empagliflozin or GLP1RA or DPP4i, based on the cohort evaluated), based on ICD-9 and -10 codes and other available data (see SEAP for details),
- Record of prescription for empagliflozin, any SGLT2i, any DPP4 inhibitor, or any GLP1RA use between 1 January 2015 and 31 December 2020, and
- No record of any prescription for the drugs being compared during the 12 months + 30-day grace preceding the index date period, i.e.,
 - o For the primary comparison of initiation of empagliflozin versus DPP4i, patients will not have any prescription for empagliflozin/any SGLT2i or DPP4i during the preceding 12 months + 30-day grace period.
 - o For the comparison of initiation of SGLT2i versus GLP1RA, patients will not have any prescription for SGLT2i or GLP1RA during the preceding 12 months + 30-day grace period.

9.2.2.2 Exclusion criteria

Exclusion criteria:

- Aged < 18 years on the first prescription date of the qualifying prescription,
- Pre-existing diagnosis of T1DM during the 12 months before the index date,
- Having a disqualifying diagnosis during the 12 months before the index date, defined as having at least one of the following: eGFR < 30 , dialysis, polycystic kidney disease or a kidney transplant,
- < 12 months of available data before the index date, and/or no complete history of drug dispensations/other records of drug use during this period, defined as not having at least 1 ambulatory visit and at least 1 medication prescription during the preceding 12 months, and
- Missing or ambiguous data on serum creatinine in the 12 months prior to the index date or sex.

[figure not shown]

Figure 1 Consort diagram of study population, the application of inclusion and exclusion criteria, and the resulting study cohorts

9.2.3 Study visits

Patients will enter the study cohort on the date of their incident prescription for empagliflozin, other SGLT2i or comparator drug (baseline date) during 2014 – 2020. Baseline data will be determined from records at the baseline encounter, and from other health system encounters up to 12 months prior to baseline (see table below for specific look back periods). Follow-up data (relevant medication prescriptions, measurements, and records for determining outcomes) will be collected until 31 December 2021 (study end date), but outcomes will be censored at 2 years after index date or end of data collection, if earlier.

Proprietary confidential information © 2023 Boehringer Ingelheim International GmbH or one or more of its affiliated companies

Table 1 Timing of patient characteristics, clinical information, and follow-up data relative to baseline

	1 Year Prior to Baseline	Baseline	+/- 3 months from baseline	+/- 30 days from baseline	Post baseline
Demographics		X			
Medication Prescriptions	X	X			X
Medical History	X				
Labs			X		X
Vitals				X	
Hospitalization Events					X
Death					X

[figure not shown]

Figure 2 Example exposure period from lookback (12 months pre-index prescription) to the post-index censoring event for a patient in the empagliflozin cohort. Example includes an event of interest (hospitalization) and the censoring time point for new GLP1RA prescription.

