
Secondary effectiveness outcomes:
 
 • Individual renal events: 40% decline in eGFR, incident ESRD, dialysis, and kidney transplant • Hospitalizations for cardiovascular events: heart failure (HF), HF+ACD, myocardial infarction+stroke+coronary revascularization+ACD, myocardial infarction+stroke+ACD • ACD 
Secondary safety outcomes:
 
 • Diabetic ketoacidosis • Severe hypoglycaemia • Urinary tract cancer • Acute kidney injury (AKI) that requires dialysis • Genital mycotic infection • Severe urinary tract infections 
Covariates: Several baseline patient characteristics will be captured in the 12 months prior to the index date. Covariates that will be included as covariates in the propensity scores (PS) model include (not are not limited to):
 
 • Demographics (age, sex, race/ethnicity, BMI, quarter and year of incident prescription, smoking status) • Comorbidities: history of heart failure, history of CV events (MI, stroke, PCI, CABG, PAD), hypertension • Prior/concomitant use of other glucose lowering agents • Prior/concomitant use of other medications e.g., cardiovascular agents (ACE/ARB, beta blocker, ARNi, statin) and diuretics • Relevant lab test results, e.g., eGFR, HbA1c, HDL-c, etc. 
Note: See Section 9.3.3 for complete list of covariates
			
Data sources:		This study will utilize high-quality renal function laboratory data available in medical electronic health records from approximately 20	

Name of company: Boehringer Ingelheim			
Name of finished medicinal product: Jardiance®			
Name of active ingredient: A10BK03 Empagliflozin			
Protocol date: 26 May 2023	Study number: 1245-0228	Version/Revision: 2.0	Version/Revision date: 26 May 2023

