	
health systems in the US that have mapped their data to the PCORnet Common Data Model (CDM). Sites meeting PCORnet data curation quality checks will be eligible to participate in this study. Sites will be approached for participation in this study based on an initial feasibility assessment to determine the extent and completeness of key data elements (renal laboratory data, prescription data, relevant medical diagnoses, and data from both inpatient and outpatient encounters). Death data will be ascertained from site records and augmented with de-identified encrypted linkage to external sources, which includes reported deaths from the government and commercial obituaries using Datavant Software.
		
Study size:	
A sample size of N=7,600 per group with median follow-up duration of 18 months will provide 80% power to detect a hazard ratio of 0.80, assuming an incidence rate of 30 per 1,000 patient years for the primary composite renal outcome in the reference cohort.
		
Data analysis:	
The index date in this study is defined as the date of the first recorded order for a qualifying prescription as a new user. Patients are required to have at least 1 ambulatory visit and at least 1 medication prescription in the 12 months prior to initiation of empagliflozin or a comparator drug (the look-back period). The look-back period includes the index date. The main analyses of this study will utilize a modified As-Treated (AT) approach and an Intention-to-Treat (ITT) approach will be used as a sensitivity analysis for the primary and secondary comparisons of the primary outcome.
 
Follow-up starts from the day after the index date until the first qualifying event has been met:
 
 • First occurrence of outcome of interest • Death • 2 years following the index prescription • End of query specific study period (December 31, 2021) • Empagliflozin user starts a DPP4i or other type of SGLT2i, or if a DPP4i user starts any SGLT2i 
 ○ SGLT2i user starts a GLP1RA, or a GLP1RA user starts any SGLT2i 		

Name of company: Boehringer Ingelheim			
Name of finished medicinal product: Jardiance®			
Name of active ingredient: A10BK03 Empagliflozin			
Protocol date: 26 May 2023	Study number: 1245-0228	Version/Revision: 2.0	Version/Revision date: 26 May 2023

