9.3.2.1 Primary renal effectiveness outcomes

Table 2 Primary outcome included in this study

Outcome	Definition
Composite outcome including 40% decline in eGFR Incident end-stage renal disease (ESRD) All-cause death	40% decline in eGFR: at least 2 measurements* during follow-up of at least a 40% decline relative to baseline separated by ≥ 28 days [R21-4243]. ESKD definition: at least 1 kidney transplant or ESKD diagnosis/procedure ¹ or at least 2 dialysis diagnoses/procedures ¹ separated by ≥ 28 days or eGFR<15 on 2 measurements separated by ≥ 28 days *The second eGFR measurement is required to be within 2 years from index, at which time, all patients will be censored (See Section

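### Table 1 lets labs and vitals measured after the index date serve as baseline, contradicting the pre-index baseline elsewhere in the protocol, and this can bias the eGFR component of the primary outcome

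*Protocol*

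**What the plan says.** Section 9.2.3 gives two accounts of baseline.

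- The text: "Baseline data will be determined from records at the baseline encounter, and from other health system encounters up to 12 months prior to baseline". It then points the reader to Table 1 with "see table below for specific look back periods".
- Table 1: Labs are marked under plus or minus "3 months from baseline" and, separately, under the post-baseline column. Vitals are marked only under plus or minus "30 days from baseline". Neither row is marked in the column for the year before baseline or in the baseline column.

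Other places bear on the same question:

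- Abstract, covariates: "Several baseline patient characteristics will be captured in the 12 months prior to the index date". eGFR, HbA1c and BMI are listed for the propensity score.
- Abstract, data analysis: "The look-back period includes the index date", with no later days mentioned. Follow-up starts the day after index.
- Section 9.2.2.2 excludes patients with "Missing or ambiguous data on serum creatinine in the 12 months prior to the index date or sex".
- Section 9.3.1 defines DKD status from the index encounter and encounters up to 12 months before it.
- Section 9.3.2.1, Table 2, defines the eGFR event as "at least 2 measurements* during follow-up of at least a 40% decline relative to baseline", without saying which value is the baseline.

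**The concern.** The Table 1 windows have to be read as baseline windows. The text sends the reader there for look-back periods, Labs have a separate post-baseline mark, and Vitals have no other mark. Read literally, a creatinine drawn up to 3 months after the first prescription, or a BMI up to 30 days after it, qualifies as a baseline value.

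Two things are at stake. First, the primary eGFR event is a percentage fall from baseline. If the drugs differ in their early effect on eGFR, a post-index baseline already carries part of that effect, and the event threshold shifts by a different amount in each arm. Second, post-index eGFR, HbA1c and BMI in the propensity score would make the weights depend on consequences of treatment. The planned balance checks would not reveal this, because they would be run on the same values. None of the sensitivity analyses that the protocol describes (intention-to-treat, matching, exclusion of the COVID period, decline on one measurement) changes the baseline window.

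**Working it through.** **Consistency of the windows**

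| Place | Baseline window |
|---|---|
| 9.2.3, text | index encounter and up to 12 months before |
| 9.2.3, Table 1, labs | 3 months before to 3 months after |
| 9.2.3, Table 1, vitals | 30 days before to 30 days after |
| Abstract, covariates | 12 months before index |
| Abstract, look-back | ends on the index date |
| 9.2.2.2, creatinine | 12 months before index |
| 9.3.1, DKD status | index encounter and up to 12 months before |

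Only Table 1 goes past the index date. Two consequences follow.

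- *Overlap.* Follow-up runs from the day after index to 24 months, so labs from the first 3 months qualify as both baseline and follow-up: 3/24 = 12.5% of the maximum follow-up.
- *Mismatch with eligibility.* A patient whose only pre-index creatinine is more than 3 and up to 12 months old is eligible. Under Table 1 that value is outside the lab window, so the patient has either a post-index baseline eGFR or none.

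**Shift of the event threshold.** No figure in the plan depends on the lab window. The sample size in section 9.5 does not use it and does not change. The early change used below is assumed.

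If the baseline is taken after an early proportional fall d, an event needs a fall of 1 − 0.6 × (1 − d) from the pre-treatment value:

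- d = 2%: 1 − 0.6 × 0.98 = 41.2%
- d = 5%: 1 − 0.6 × 0.95 = 43.0%
- d = 10%: 1 − 0.6 × 0.90 = 46.0%

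In absolute terms, with a true value of 60 mL/min and an early fall of 4, the event line moves from 0.6 × 60 = 36.0 to 0.6 × 56 = 33.6. An early rise would move it the other way.

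**Effect on the eGFR component.** A simulation used 400,000 patients per arm, baseline eGFR N(75, 20) truncated at 30, slope N(−4, 8) per year, measurement SD 6, labs every 4 months, and an event at two consecutive values at or below 60% of baseline. It assumed an early reversible fall of 2 to 5 mL/min on empagliflozin only, and a post-index baseline in 25% to 50% of patients. The risk ratio for confirmed decline was multiplied by 0.85 to 0.96. An independent run on the same inputs, with post-index labs spread over 3 months, gave 0.87 to 0.97.

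**Effect on the composite.** Let q be the share of the empagliflozin arm affected, w the share of composite events that are eGFR decline, and r the multiplier on eGFR-event risk in an affected patient. Approximately:

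observed HR = true HR × [1 − q × w × (1 − r)]

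Assumed ranges: q 10% to 50%, w 30% to 70%, r 0.7 to 0.9. The range for r fits the simulation: a multiplier of 0.93 at q = 50% (fall of 2) implies r = 1 − 0.07/0.50 = 0.86, and 0.85 at q = 50% (fall of 5) implies r = 1 − 0.15/0.50 = 0.70.

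- Mildest case: 1 − 0.10 × 0.30 × 0.10 = 0.997. A true 1.00 reads 0.997, and a true 0.80 reads 0.798.
- Strongest case: 1 − 0.50 × 0.70 × 0.30 = 0.895. A true 1.00 reads 0.895, and a true 0.80 reads 0.716.

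**The case against.** The strongest reply is that this is one faulty table and not a chosen design. Every other statement is pre-index, and the text calls the windows look-back periods. That stands, and it is why the point is put as a contradiction. It does not dispose of the point, because the text defers to the table and no other place in the protocol gives a specific window for labs or vitals. The SEAP may define the reference eGFR, but a window stated in the protocol is not a detail left to the SEAP.

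Three stronger readings are tempting, and the protocol does not support them.

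- *The primary result is biased in favour of empagliflozin.* Table 1 gives a window but no rule for choosing among values in it. Under a last-value-before-index rule, only patients without a creatinine in the preceding 3 months would take a later one. The protocol gives neither that share nor the early eGFR change by arm.
- *The primary outcome is distorted by 0.85 to 0.96.* That range is for eGFR decline alone, with an unsourced 25% to 50% post-index share. The simulated reference-arm risk was about 6.8% over 2 years, or −ln(1 − 0.068)/2 ≈ 35 per 1,000 patient-years. Section 9.5 assumes 30 for the whole composite, so the model overweights this component. Death does not use the baseline eGFR. With a post-index share of 5% to 10%, the same model gives a composite multiplier of 0.98 to 0.997.
- *Patients must survive to a post-index lab to be analysed.* Table 1 permits such a lab and does not require it. Every eligible patient has a pre-index creatinine, and section 9.6 allows imputation or redefinition of missing covariates. The issue is confined to patients whose only creatinine is more than 3 months old, and only if the table is applied literally.

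**Conclusion.** Table 1 is wrong as written: its symmetric windows contradict the pre-index baseline in the text above it, the abstract, section 9.2.2.2 and section 9.3.1. That conclusion needs no assumption. If the table is followed, post-treatment values can become the reference eGFR and propensity covariates, which can bias the eGFR component and hence the composite.

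The size is unknown. The composite range of 0.997 to 0.895 for a true hazard ratio of 1.00 runs from negligible to material. It rests on the assumed q, w and r and on an early eGFR fall confined to the empagliflozin arm. It is an illustration and not a bound. The correction is still needed before the comparative analysis, because the reference value of the primary renal event is left in contradiction.

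**What to change.** - In Table 1, remove the post-index half of both windows, so that baseline labs and vitals come only from on or before the index date.
- In Table 2 (section 9.3.2.1), define the reference eGFR as the most recent value on or before index within the 12-month look-back already used for creatinine eligibility and DKD status.
- State that later values count only as follow-up.

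The length of the pre-index window for vitals and for the other labs is a separate choice between recency and completeness. It may stay shorter than 12 months if the sponsor prefers. If a symmetric window is of interest, it belongs in a labelled sensitivity analysis.

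The cost is more than a table edit. Section 6 puts the end of data collection in July 2022, and the amendment log shows that Phase 1 results had already been reviewed. Baseline covariates, propensity scores, overlap weights and balance checks would have to be re-derived. Some baseline values would be older or more often missing.
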